3. STUDY DESIGN

3.1. General Design

This is a Phase 3b, open-label study to evaluate the safety, reactogenicity, and immunogenicity of mRNA-1273 SARS-CoV-2 vaccine in SOT recipients and healthy controls. Adult kidney and liver transplant recipients and healthy control participants who are at least 18 years of age will be enrolled.

Approximately 240 adult participants (220 previously vaccinated or unvaccinated participants who have had a kidney or liver transplant and 20 unvaccinated healthy adults) will be enrolled. At least 50 SOT recipients who completed primary vaccination series with a non-Moderna COVID-19 vaccine under EUA (outside of the mRNA-1273-P304 study) will be enrolled in Part B (Group B4).

In Part A, all SOT recipients who were unvaccinated prior to enrollment will receive 2 doses of 100 µg of mRNA-1273 (vaccine) 28 days apart (window of -3/+7 days for the second dose) (Group A1). The SOT recipients will be offered the opportunity to receive a third primary dose of vaccine at Day 85 (window of -3/+7 days for the third dose) as per the EUA Fact Sheet available at the time of protocol finalization (Group A2). All healthy participants will receive 2 doses of vaccine 28 days apart (window of -3/+7 days for the second dose) (Group A5). SOT recipients who were previously vaccinated with 2 doses of Moderna COVID-19 vaccine under the EUA prior to enrollment will receive dose 3 on Day 1 (Group A3). These participants will be referred to as previously vaccinated throughout this document. Under Amendment #4, unvaccinated SOT participants who will be enrolled will be given 3 100 µg doses in Part A then proceed to Part B to receive a 100 µg booster dose. Under Amendment #4, SOT participants previously vaccinated with 2 doses of Moderna COVID-19 vaccine outside of the study who will be enrolled will receive a third 100 µg dose in Part A then proceed to Part B to receive a 100 µg BD.

In Part B, all eligible active participants in Part A will be offered to receive a 100 µg BD of mRNA-1273 who are at least 4 months from the last dose. SOT recipients who completed primary COVID-19 vaccination series under EUA will receive a 100 µg BD on BD-D1.

The schematic of study arms and major study events is illustrated in [Figure 1](#), [Figure 2](#), [Figure 3](#), and [Figure 4](#). The schedules of events (SoEs) for the study are presented in [Section 10.1](#). Study arms and doses are presented in [Table 2](#).

[figure not shown]
Table 2: Study Arms

Study Arm	Part A	Doses in P304 Part A	Part A Dose	Move on to Part B?	Part B	Doses in P304 Part B	Part B B-Dose	Total Doses in P304
SOT Recipient Cohorts								
Unvaccinated participants who consent to receive only 2 doses in Part A (Days 1 and 29)	Group A1	2	100 µg		NA	N/A	N/A	2
Unvaccinated participants who consent to receive 3 doses in Part A (Days 1, 29, and 85)	Group A2	3	100 µg	➡	Group B2	1	100 µg	4
Participants previously vaccinated with 2 doses of the Moderna COVID-19 vaccine under the EUA who consent to receive a third dose in Part A (Day 1)	Group A3	1	100 µg	➡	Group B3	1	100 µg	2
SOT recipients who completed primary vaccination with an mRNA or non-mRNA COVID-19 vaccine outside mRNA-1273-P304 who consent to receive 1 booster dose (in Part B)	N/A	N/A	N/A		Group B4	1	100 µg	1

Study Arm	Part A	Doses in P304 Part A	Part A Dose	Move on to Part B?	Part B	Doses in P304 Part B	Part B B-Dose	Total Doses in P304
Healthy Adult Cohort								
Healthy adults who consent to receive 2 doses in Part A (Days 1 and 29)	Group A5	2	100 µg	➡	Group B5	1	100 µg	3

[figure not shown]
Abbreviations: B-Dose = booster dose; EUA = Emergency Use Authorization; SOT = solid organ transplant,

Figure 1: Study Schema for Unvaccinated Participants Who Receive the 2-Dose Vaccination Regimen (Part A)

[figure not shown]
Abbreviations: CMI = cell-mediated immunity; IA = interim analysis; immuno = immunogenicity; NP = nasopharyngeal; SOT = solid organ transplant (recipients).

Figure 2: Study Schema for Unvaccinated Participants Who Receive the 3-Dose Vaccination Regimen (Part A)

Abbreviations: CMI = cell-mediated immunity; NP = nasopharyngeal; SOT = solid organ transplant (recipients).

**Figure 3: Study Schema for Previously Vaccinated Participants Who Receive a Single-dose Vaccination Regimen (dose 3)
(Part A)**

Abbreviations: CMI = cell-mediated immunity; NP = nasopharyngeal; SOT = solid organ transplant.

Figure 4: Booster Phase Study Pathway

[figure not shown]
[figure not shown]

Figure 5: Study Schema for Booster Dose Phase (Part B)

For Part A, the primary immunogenicity goal of the study is to evaluate serum Ab responses obtained 28 days after the second or third dose of vaccine (Day 57 for unvaccinated participants of the 2-dose regimen, Day 113 for unvaccinated SOT participants of the 3-dose regimen, and Day 29 for previously vaccinated SOT participants of dose 3). Using the Ab threshold established from Study P301 (if available at the time of database lock), an additional exploratory analysis will be performed by measuring the proportion of participants with a serum Ab level at Day 57 (for unvaccinated participants of 2-dose regimen), Day 113 (unvaccinated SOT recipients of 3-dose regimen), and Day 29 (previously vaccinated SOT recipients of dose 3) greater than or equal to the Ab threshold of protection against COVID-19, with a 2 sided 95% CI using the Clopper Pearson method by cohort arm.

This study will monitor participants for a total of up to 12 months (12 months after their last dose of vaccine for participants not receiving a BD or 6 months after their BD). The SOT participants who do not consent to receive a third dose of mRNA-1273 (Group A1) and healthy adult participants (Group A5) will be monitored for a total of 12 months after their second dose. Safety assessments will include solicited local and systemic ARs for 7 days after each dose; unsolicited AEs for 28 days after each dose; MAAEs; SAEs; AESIs, AEs leading to discontinuation from dosing and/or study participation (withdrawal) from dose 1 through the end of study (EOS); concomitant medications associated with AEs, MAAEs, or COVID-19 or SARS-CoV-2 infection; participant experience of COVID-19 symptoms; biopsy-proven organ rejection; safety laboratory assessments; vital sign measurements; and physical examination findings as presented in the applicable SoE ([Section 10.1](#)).

From all unvaccinated SOT participants who receive 3 doses of mRNA-1273 (Group A2), blood samples will be collected at baseline (Day 1), Day 29 (28 days after dose 1), Day 57 (28 days after dose 2), Day 85 (dose 3), Day 113 (28 days after dose 3), Day 265 (6 months after dose 3), and Day 450 (12 months after dose 3).

From unvaccinated participants who receive 2 doses of vaccine (healthy adults [Group A5] and SOT recipients who decline to receive a third dose [Group A1]), blood samples will be collected at baseline (Day 1), Day 29 (28 days after dose 1), Day 57 (28 days after dose 2), Day 209 (6 months after dose 2), and Day 394 (12 months after dose 2).

From previously vaccinated SOT participants who receive 1 dose of mRNA-1273 (Group A3), blood samples will be collected at pre-dose 3 (Day 1), Day 29 (28 days after dose 3), Day 180 (6 months after dose 3), and Day 365 (12 months after dose 3).

These blood samples will be for the assessment of the following endpoints and analytes:

- Measurement of SARS-CoV-2-specific bAb and nAb responses

- Development of Ab directed against nonvaccine antigen (nucleocapsid protein), which will signify infection with SARS-CoV-2. Participants who tested positive for Ab against SARS-CoV-2 nucleocapsid protein at baseline can continue in the study.

From unvaccinated SOT participants (Group A1 and Group A2), blood samples for cell-mediated immunity (CMI) studies will also be collected at Day 1, Day 36, and Day 92 (SOT recipients receiving 3 doses [Group A2]) from a subset of up to 50 SOT participants, as well as, from 20 healthy controls (Group A5) (Day 1 and Day 36), and from a subset of at least 50 previously vaccinated SOT recipients (Group A3) at Day 1 and Day 8, for exploratory assessments to characterize T- and B-cell responses to vaccine.

The NP swab samples obtained at illness visits ([Section 7.3.1](#)) will be used as sources of SARS-CoV-2 for genetic sequencing.

SARS-CoV-2 bAb against the nonvaccine antigen (nucleocapsid protein) will also be collected at the Illness and Convalescent visits.

The number of cases of COVID-19 will be assessed throughout the study ([Section Error! Reference source not found.](#)). Once a participant is identified as a case of COVID-19, a convalescent visit will be scheduled approximately 28 days after the confirmed diagnosis for a clinical evaluation and immunologic assessment of SARS-CoV-2 infection.

For unvaccinated SOT recipients (Group A1 and Group A2), laboratory assessments for safety related to kidney function for kidney SOT recipients (serum creatinine, urine protein, and UPCR) and liver function for liver SOT recipients (alanine aminotransferase [ALT], aspartate aminotransferase [AST], alkaline phosphatase [ALP], and bilirubin) will be monitored on Day 1, Day 8, Day 29, Day 36, and Day 57 for SOT recipients who receive 2 doses only (Group A1) and on additional Days 85, 92, and Day 113 for SOT recipients who receive 3 doses (Group A2).

For previously vaccinated SOT recipients (Group A3), laboratory assessments for safety will be monitored on Day 1 (dose 3), Day 8, and Day 29.

After Day 57 (for unvaccinated SOT participants who receive 2 doses [Group A1]) or after Day 113 (for unvaccinated SOT participants who receive 3 doses [Group A2]), or after Day 29 (for previously vaccinated SOT recipients who receive dose 3 [Group A3]), the investigator will review standard-of-care laboratory assessments related to kidney and liver function and report any laboratory-related AEs and suspected or confirmed events of organ transplant rejection until the EOS.

Part B - Booster Phase

Part B is designed to offer participants in Part A, who are at least 4 months from the last dose, the option to request a BD (100 µg) of the prototype mRNA-1273 (Group B2, Group B3, and

Group B5). Part B is also designed to enroll SOT participants who completed primary vaccination series with mRNA or non-mRNA COVID-19 vaccine under the EUA who are at least 4 months from last dose (Table 3). At least 50 SOT recipients who completed primary vaccination series with a non-Moderna COVID-19 vaccine under the EUA (outside of the mRNA-1273-P304 study) will be enrolled in Part B. In case a variant of concern emerges and available data show a decreased immune response after vaccination with the prototype 100 µg BD, the Part B Booster Phase may test or replace the prototype 100 µg BD with a variant-specific mRNA-1273 vaccine (ie, Omicron-specific or mRNA-1273.529).

Table 3: Primary Series Vaccination for Booster Dose Eligibility

Primary Series Vaccine	Primary Series Number of Doses
mRNA COVID-19 vaccine (ie, Moderna, Pfizer)	3 doses
Non-mRNA COVID-19 vaccine (ie, Janssen)	2 doses or at least 1 dose combined with an mRNA COVID-19 vaccine

If eligible, each study participant in Part A will receive a notification letter and will be asked to schedule a BD-1 visit at their study site. Principal Investigators should consider current local public health guidance for administration of COVID-19 vaccines under EUA and marketing authorization (if any) when determining the scheduling priority of participants.

At the BD-1 visit, each participant will:

- Each study participant in Part A will be encouraged to remain in the ongoing study,
- Sign a revised informed consent form (ICF) that includes both updated safety information relevant to the ongoing study and a BD.
 - Participants from Part A will be offered the option to receive a 100 µg BD (Group B2 and Group B3),
 - Eligible SOT participants who completed the primary vaccination series under EUA will be given a 100 µg BD of mRNA-1273 (Group B4),
 - Under Amendment #4, unvaccinated SOT participants who will be enrolled will be given 3 100 µg doses in Part A then proceed to Part B to receive a 100 µg booster dose.
 - Under Amendment #4, SOT participants previously vaccinated with 2 doses of Moderna COVID-19 vaccine outside of the study who will be enrolled will receive a third 100 µg dose in Part A then proceed to Part B to receive a 100 µg BD.

- Be counselled about the importance of continuing other public health measures to limit the spread of disease including social distancing, wearing a mask, and hand-washing.

At the BD-1 visit, participants will have the following study site visits and complete scheduled activities according to the Part B SoE:

- BD-1 visit: Participants will receive a single 100 µg dose of mRNA-1273
- BD-1a visit: Day 4, 3 days after BD on Day 1
- BD-2 visit: Day 8, 7 days after BD on Day 1
- BD-3 visit: Day 29, 28 days after the BD on Day 1
- BD-4 visit: Day 181, 180 days after the BD on Day 1

3.1.1. Study Periods

There will be 3 study periods: a Screening Period, a Treatment Period, and a Follow-up Period.

For unvaccinated SOT and Healthy participants who receive the 2-dose vaccine regimen in Part A (Group A1 and Group A5):

The study comprises 8 scheduled visits, including a screening visit and 7 scheduled clinic visits. Electronic diary (eDiary) recording of solicited local and systemic reactogenicity ([Section 7.5.3](#)) will occur on the day of each injection and for 6 days following injection. Safety follow-up via an eDiary questionnaire will be performed every 4 weeks from Day 71 to Day 183 and again from Day 223 to Day 363. Additional safety follow-up via a safety telephone call will be performed every 4 weeks from Day 85 to Day 197 and again from Day 237 to Day 377. If the last dose is delayed, additional safety calls every 4 weeks should be scheduled when the gap between the safety call scheduled on D377 and the last study visit is beyond 28 days.

Per participant, the study duration will be approximately 13 months, which includes 1 week for screening (Day -7 to Day 1), 28 days for dosing (on Day 1 and Day 29), and 12 months of follow-up after the second dose to monitor for safety, immunogenicity, and breakthrough SARS-CoV-2 infection or COVID-19. Day 0 and Day 1 may be combined on the same day ([Table 7](#)).

For unvaccinated participants who receive the 3-dose vaccine regimen in Part A (Group A2):

The study comprises 11 scheduled visits, including a screening visit and 10 scheduled clinic visits. eDiary recording of solicited local and systemic reactogenicity ([Section 7.5.3](#)) will occur on the day of each injection and for 6 days following injection. Safety follow-up via an eDiary questionnaire will be performed every 4 weeks from Day 127 to Day 239 and again from Day 279 to Day 419. Additional safety follow-up via a safety telephone call will be performed every

4 weeks from Day 141 to Day 253 and again from Day 293 to Day 433. If the last dose is delayed, additional safety calls every 4 weeks should be scheduled when the gap between the safety call scheduled on D433 and the last study visit is beyond 28 days.

Per participant, the study duration will be approximately 15 months, which includes 1 week for screening (Day -7 to Day 1), 3 months for dosing (on Day 1, Day 29, and Day 85), and 12 months of follow-up after the third dose to monitor for safety, immunogenicity, and breakthrough SARS-CoV-2 infection or COVID-19. Day 0 and Day 1 may be combined on the same day ([Table 8](#)).

For previously vaccinated participants who receive the single-dose vaccination regimen (dose 3) in Part A (Group A3):

The study comprises 6 scheduled visits, including a screening visit and 5 scheduled clinic visits. eDiary recording of solicited local and systemic reactogenicity ([Section 7.5.3](#)) will occur on the day of injection and for 6 days following injection. Safety follow-up via an eDiary questionnaire will be performed every 4 weeks from Day 43 to Day 155 and again from Day 194 to Day 306. Additional safety follow-up via a safety telephone call will be performed every 4 weeks from Day 57 to Day 169 and again from Day 208 to Day 320.

Per participant, the study duration will be approximately 12 months, which includes 1 week for screening (Day -7 to Day 1), and 12 months of follow-up after dose 3 to monitor for safety, immunogenicity, and breakthrough SARS-CoV-2 infection or COVID-19. The screening visit and Day 1 may be combined on the same day ([Table 9](#)).

For participants who receive the BD in Part B (Group B2, Group B3, Group B4, and Group B5):

The study comprises 5 scheduled clinic visits and 6 safety calls (BD-D15, BD-D22, BD-D59, BD-D89, BD-D119, and BD-D149).

Per healthy participant receiving 2 doses of mRNA-1273 in Part A (Group B5) who consent to receive BD, the study duration will be approximately 10 months, which includes 1 week for screening (Day -7 to Day 1), 4 months for dosing (on Day 1, Day 29, and Day 129 for BD), and 6 months of follow-up after the BD to monitor for safety, immunogenicity, and breakthrough SARS-CoV-2 infection or COVID-19.

Per SOT study participant who received 3 doses of mRNA-1273 in Part A (Group B5) who consent to receive BD, the study duration will be approximately 13 months which includes 1 week for screening (Day -7 to Day 1), 7 months of dosing (on Day 1, Day 29, Day 85, and Day 205 for BD) and 6 months of follow-up after BD to monitor for safety, immunogenicity, and breakthrough SARS-CoV-2 infection or COVID-19.

Per SOT study participant who previously received 2 doses under EUA, enrolled in Part A to receive a third dose (Group B3) and who consent to receive a BD, the study duration will be approximately 10 months which includes 1 week for screening (Day -7 to Day 1), 4 months of dosing (Day 1 [dose 3] and Day 120 [BD]) and 6 months of follow-up after BD to monitor for safety, immunogenicity, and breakthrough SARS-CoV-2 infection or COVID-19.

Per SOT study participant who previously completed primary vaccination series (3 doses) under EUA (Group B4), the study duration will be approximately 6 months which includes 1 week for screening (Day -7 to Day 1), 1 day for dosing and 6 months of follow-up after BD to monitor for safety, immunogenicity, and breakthrough SARS-CoV-2 infection or COVID-19.

This study will be conducted in compliance with the protocol, Good Clinical Practice (GCP), and all applicable regulatory requirements ([Section 10.2.1](#)).

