The CEAC will operate under the rules of an approved charter that will be written and reviewed at the organizational meeting of the CEAC. Details regarding the CEAC composition, responsibilities, procedures, and frequency of data review will be defined in its charter.

In addition, an Internal Safety Team (IST) will be created specifically to review safety and reactogenicity data after:

- At least 10 SOT recipients have received their third dose of study vaccine (Group A2 and Group A3) and have at least 7 days of reactogenicity data
- At least 55 SOT recipients have received their third dose of study vaccine (Group A2 and Group A3), unless a safety event requires earlier review
- Any other ad hoc safety concerns based on ongoing safety surveillance

The IST will operate under the rules of an approved charter that will be written and reviewed at the organizational meeting of the IST. Details regarding the IST composition, responsibilities, procedures, and frequency of data review will be defined in its charter.

Study Duration:

Part A:

Per participant receiving 2 vaccine doses (Group A1), the study duration will be approximately 13 months, which includes 1 week for screening, 1 month for dosing, and 12 months of follow-up after the second dose to monitor for safety, immunogenicity, and breakthrough SARS-CoV-2 infection or COVID-19.

Per participant receiving 3 vaccine doses (Group A2), the study duration will be approximately 15 months, which includes 1 week for screening, 3 months for dosing, and 12 months of follow-up after the third dose to monitor for safety, immunogenicity, and breakthrough SARS-CoV-2 infection or COVID-19.

Per participant receiving 1 vaccine dose only (dose 3) (Group A3), the study duration will be approximately 12 months, which includes 1 week for screening, 1 day for dosing, and 12 months of follow-up after dose 3 to monitor for safety, immunogenicity, and breakthrough SARS-CoV-2 infection or COVID-19.

Part B – Booster Phase

Per healthy participant receiving 2 doses of mRNA-1273 in Part A (Group B5), the study duration will be approximately 10 months, which includes 1 week for screening (Day -7 to Day 1), 6 months for dosing (on Day 1, Day 29, and Day 129 for BD), and 6 months of follow-up after the BD to monitor for safety, immunogenicity, and breakthrough SARSCoV2 infection or COVID-19.

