3.1.1.2. Treatment Period and Follow-up Period

The Treatment Period for each participant starts with Day 1 and is scheduled to end 28 days after each dose of vaccine. In Part A, for unvaccinated SOT and healthy participants who receive the 2-dose regimen (Group A1 and Group A5), the Follow-up Period starts with Day 58 and is scheduled to end on Day 394 (12 months after the second dose). The Follow-up Period for unvaccinated SOT participants who receive the 3-dose regimen (Group A2) starts with Day 114 and is scheduled to end on Day 450 (12 months after the third dose). The Follow-up Period for previously vaccinated participants (Group A3) starts with Day 29 and is scheduled to end on Day 365 (12 months after dose 3). In Part B (Group B2, Group B3, Group B4, and Group B5), Follow-up Period starts with Day 29 and is scheduled to end on BD-D181 (6 months after BD).

For Part A (Group A1, Group A2, Group A3, and Group A5): On Day 1, after the completion of the scheduled assessments ([Section 10.1](#)), all participants will be administered a single IM dose of 100 μ g of mRNA-1273 ([Section 5.3.2](#)). Participants will be closely monitored for safety and will remain at the study site for observation for at least 30 minutes after dosing. For unvaccinated SOT and healthy participants (Group A1, Group A2, and Group A5), the second dose of vaccine will be administered on Day 29. Unvaccinated SOT recipients who consent to receive a third dose of

vaccine (Group A2) will receive it on Day 85. Previously vaccinated SOT recipients (Group A3) will receive dose 3 on Day 1. Participants will be monitored for 12 months after the second and third dose (as applicable) of vaccine for safety, immunogenicity, and breakthrough SARS-CoV-2 infection or COVID-19.

For Part B (Group B2, Group B3, Group B4, and Group B5): On BD-D1, after the completion of the scheduled assessments, at least 4 months after the last dose, all participants will be administered a single intramuscular (IM) dose of 100 µg BD of mRNA-1273. Participants will be closely monitored for safety and will remain at the study site for observation for at least 30 minutes after dosing. Participants will be monitored for 6 months after the BD for safety, immunogenicity, and breakthrough SARS-CoV-2 infection or COVID-19.

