4.2. Study Eligibility Criteria (Part B)

4.2.1. Inclusion Criteria (Group B2, Group B3, Group B4, and Group B5)

1. a. Participants must have been previously enrolled in the mRNA-1273-P304 study, are actively participating in Part A and are at least 4 months from the last dose, or
b. Is an adult male or female individual, at least 18 years of age at the time of signing informed consent, is EITHER a kidney or a liver (single organ) transplant recipient who

is at least 90 days after transplantation at the time of consent AND who completed primary vaccination series (3 doses for mRNA COVID-19 vaccine; 2 doses for non-mRNA COVID-19 vaccine or at least 1 dose of non-mRNA combined with 1 dose of mRNA COVID-19 vaccine) under the EUA who are at least 4 months from the last dose. All primary COVID-19 vaccination series must be completed after transplant.

2. Female participants of childbearing potential may be enrolled in the study if the participant has a negative pregnancy test on the day of the booster dose injection (BD-Day 1).

4.2.2. Exclusion Criteria (for Participants who Completed Primary Vaccine Series under EUA) (Group B4)

Exclusion Criteria in Part A will apply except prior or planned administration of a coronavirus vaccine and current treatment with investigational agents for either prophylaxis against COVID 19.

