17. Trained study site personnel will call all participants to collect information relating to any AEs, MAAEs, SAEs, AESIs, AEs leading to discontinuation from dosing and/or study participation withdrawal, information on concomitant medications associated with those events, and any nonstudy vaccinations. In addition, study personnel will collect information on known participant close contact exposure to someone with known COVID-19 or SARS-CoV-2 infection and on participant experience of COVID-19 symptoms.
18. All concomitant medications and nonstudy vaccinations will be recorded through 28 days after injection; all concomitant medications relevant to or for the treatment of an SAE, confirmed (biopsy-proven) or suspected events of organ transplant rejection, or MAAE will be recorded from Day 1 through the final visit (Day 365). In addition, the 2 previous doses of the Moderna COVID-19 vaccine will be recorded in the participant's eCRF regardless of the timing.
19. All immunosuppressant medications, for 3 months prior to Screening and throughout the study. Any change in the maintenance therapy should be recorded and the reason for the change documented.

Table 10: Booster Dose Phase (Part B: Group B2, Group B3, Group B4, and Group B5)

Visit Number	BD-1	BD-1a	BD-2	-	BD-3	-	BD-4
Type of Visit	C	C	C	SC	C	SC	C
Study Visit Day	BD-D1 ¹ (D205 for SOTr who received 3 doses; D120 for SOTr who received 1 dose; D149 for healthy cohort; at least 4 mos from last dose for SOTr who received primary series under EUA)	BD-D4	BD-D8	14 and 21 days after BD-D1 (BD-D15, BD-D22)	BD-D29	BD-D59, BD-D89, BD-D119, BD-149	BD-D181
Window Allowance (Days)	- 14 days	-2	+3	+3	-3/+14	+3	-3/+14
Days Since Most Recent Vaccination (in Part B)	0	3	7	-	28	-	180
Informed consent form, demographics, concomitant medications, medical history	X						
Review of inclusion and exclusion criteria	X						
Physical examination including height and weight ²	X				X		X
Lymph node assessment ³	X		X				
Vital signs ⁴	X		X		X		X
Pregnancy testing ⁵	X						
Immunogenicity Assessment							
Blood for immunologic analysis and assessment of Ab against nonvaccine antigen ⁶	X				X		X

Visit Number	BD-1	BD-1a	BD-2	-	BD-3	-	BD-4
Type of Visit	C	C	C	SC	C	SC	C

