Recording of suspected AND confirmed organ transplant rejection ¹⁷	X	X	X	X	X	X	X
Recording of concomitant medications and nonstudy vaccinations ¹⁷	X	X	X	X	X	X	X
Recording of concomitant immunosuppressant medications ¹⁸	X	X	X	X	X	X	X

Abbreviations: AE = adverse event; AESI = adverse event of special interest; AR = adverse reaction; BD = booster dose; C = clinic visit; D = day; eDiary = electronic diary; ICF = informed consent form; MAAE = medically attended AE; NP = nasopharyngeal; SAE = serious adverse event; SC = safety (phone) call; SOTr = solid organ transplant recipients.

Note: In accordance with FDA Guidance on Conduct of Clinical Trials of Medical Products during COVID-19 Public Health Emergency (DHHS 2020), investigators may convert study site visits to home visits or telemedicine visits with the approval of the Sponsor.

1. A BD may be administered to all eligible participants who are currently enrolled in Part A or Part B provided there are no current contraindications for further dosing ([Section Error! Reference source not found.](#)). A participant who is currently in the Convalescent Period may come in for a BD-1 visit and receive a BD as long they are no longer symptomatic, and this includes the possibility for a Convalescent Visit Day 28 to overlap and be combined with a BD-1 visit. For eligible participants in Part A who are at least 4 months from completion of primary vaccination series who consent to receive BD, the study visit or follow-up 4 months after their last dose in Part A may overlap with BD-D1. In this case, a participant will need to come in for the BD-D1 visit at least 4 months after the last dose and then follow Part B.

2. Symptom-directed physical examination will be performed at the BD-Day 1. At visits BD-2 (BD-D29), and BD-3 (BD-D181), a symptom-directed physical examination may be performed at the discretion of the investigator. Any clinically significant finding identified during a study visit should be reported as a MAAE.
3. On dosing day before injection, the arm receiving the injection should be examined and the associated lymph nodes should be evaluated.

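### The protocol prints two booster days for the healthy cohort (Group B5), Day 129 and D149, and Day 129 conflicts with its own four-month minimum interval

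*Protocol*

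**What the plan says.** **Booster day for the healthy cohort**
- Protocol section 3.1.1 and the synopsis under Study Periods: "4 months for dosing (on Day 1, Day 29, and Day 129 for BD".
- Protocol synopsis under Study Duration: "6 months for dosing (on Day 1, Day 29, and Day 129 for BD". The days are the same, but the dosing period is longer.
- Protocol Table 10 (section 10.1), column heading for the BD-1 visit: "D149 for healthy cohort", with a window of -14 days.

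**Last Part A dose.** For the healthy cohort, section 3.1.1.2 states that "the second dose of vaccine will be administered on Day 29".

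**Minimum interval.** The rule appears in three kinds of text:
- Eligibility, section 4.2.1, criterion 1a: participants "are actively participating in Part A and are at least 4 months from the last dose".
- Dosing, section 3.1.1.2, in a paragraph that names Group B5: "at least 4 months after the last dose, all participants will be administered".
- Table 10, footnote 1: "a participant will need to come in for the BD-D1 visit at least 4 months after the last dose".

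**SAP.** Sections 5.3.2 and 5.3.3 make receipt of the booster according to schedule a condition of the Part B per-protocol sets, without stating a day. Section 6.1 takes the schedule from Appendix 1 of Protocol Amendment 4. SAP Appendix E cites a Table 18 in that appendix. The protocol's list of tables ends at Table 13, and the Part B schedule is Table 10.

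**The concern.** Two different planned days cannot both be the schedule. One of them also appears to fall inside an interval that the protocol's eligibility rule forbids, and section 4 of the protocol does not permit waivers of enrollment criteria.

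A site that booked booster visits from the synopsis or section 3.1.1 could create two deviations at once. One is of timing, because section 5.4 classes a visit outside its window as a deviation. The other is of eligibility.

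At stake are the healthy participants' Part B data: cell-mediated immunity (CMI), for which the healthy cohort is the biological control, safety, and descriptive antibody results. The group is small, since only 20 healthy adults are planned.

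**Working it through.** **Inputs.** Dose 2 on Day 29 (section 3.1.1.2), with a -3/+7 day window (section 3.1). Booster on Day 129 (synopsis, section 3.1.1) or D149 (Table 10). Table 10 window -14 days. Follow-up of 180 days after the booster. Screening of 7 days. Average month = 365.25/12 = 30.44 days.

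**1. Interval from last dose = booster day - day of last dose**

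| Case | Days | Average months |
|---|---|---|
| Day 129 - Day 29 | 100 | 3.29 |
| D149 - Day 29 | 120 | 3.94 |
| Earliest day in the Table 10 window: 149 - 14 = D135; 135 - 29 | 106 | 3.48 |
| Day 129, dose 2 at the early limit, Day 26 | 103 | 3.38 |
| Day 129, dose 2 at the late limit, Day 36 | 93 | 3.06 |

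**2. Comparison with four months.** The documents do not define a month, so three readings were tried.
- Calendar months: 120 to 123 days. Day 129 is 20 to 23 days short.
- Average months: 4 x 30.44 = 121.75 days. Day 129 is 21.75 days short.
- 28-day months: 4 x 28 = 112 days. Day 129 is 12 days short.

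Day 129 passes four months only if counted from dose 1: 129 - 1 = 128 days, or 4.21 months. The rule counts from the last dose. D149, at 120 days, meets four months as 4 x 30 and is 0 to 3 days short by calendar.

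**3. The other cohorts.** Section 3.1.1 gives the 3-dose transplant group "7 months of dosing (on Day 1, Day 29, Day 85, and Day 205 for BD": 205 - 85 = 120 days. Group B3 has Day 120 after a dose on Day 1: 119 days. Both days match Table 10. Only the healthy cohort's day differs between text and table. Section 3.1.1 labels that 3-dose transplant paragraph Group B5, where the synopsis has Group B2, so a reader looking up B5 there finds two booster days.

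**4. Durations for the healthy cohort**
- Synopsis Study Periods and section 3.1.1: 7 days + 4 months + 6 months = 0.23 + 4 + 6 = 10.23 months. This agrees with the stated total of about 10.
- Synopsis Study Duration: 0.23 + 6 + 6 = 12.23 months. This does not agree with the same stated total of about 10.
- From the days: (7 + 128 + 180)/30.44 = 10.35 months with Day 129, and (7 + 148 + 180)/30.44 = 11.01 months with D149.

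The total of about 10 months therefore fits Day 129 better, so changing a day in one place would leave the duration text to be checked as well.

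**The case against.** The strongest reply is that the documents largely settle what sites must follow. All three Day 129 entries are parentheses inside estimates of study duration, not dosing instructions. Section 7 requires procedures and their timing to follow section 10.1. Table 7, footnote 3, sends 2-dose participants who accept a booster to Table 10. The minimum interval is stated repeatedly as an operative rule, and eligibility is checked at the booster visit. This stands, and it limits the practical risk. It does not remove the contradiction, because a protocol should not print three times a day that its own criterion excludes.

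A reader might infer more than the documents support:

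- *That healthy controls will be boosted about 20 days early.* This assumes that a site puts a duration estimate ahead of the schedule and the eligibility check. Nothing shows that.
- *That they will drop out of the Part B per-protocol immunogenicity set and the CMI control will be lost.* SAP section 6.1 takes its schedule from Appendix 1, which contains Table 10. SAP section 5.3.3 names that set as primary for binding and neutralizing antibody data, and the documents do not say that leaving it removes someone from the CMI summaries. Part B analysis windows run from the actual booster date (SAP Table 3, footnote 5), so BD-Day 29 and BD-Day 181 do not move.
- *That a shorter interval biases a comparison with transplant recipients.* Protocol section 8.1 plans no between-group comparisons. The SAP already summarizes the time from the last Part A injection to the booster (section 6.2.6).
- *That all 20 healthy participants are affected.* Twenty is an upper bound. Amendment 4 is dated 20 December 2021, and first enrollment was estimated for April 2021. Anyone first dosed by 14 August 2021 had reached Day 129 by the amendment date (128 days later). Enrollment dates are not given, so the range is 0 to 20.
- *That D149 must be correct.* The -14 day window on D149 itself allows 106 days, which also sits awkwardly with four months. The documents do not settle the matter.

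**Conclusion.** The point holds as an internal inconsistency. The healthy cohort's booster is printed at 100 days after dose 2 in three places and at 120 days in Table 10. The 100-day figure conflicts with the four-month minimum by 12 to 23 days, depending on how a month is counted, and lies 6 days before the earliest visit that Table 10 allows. The dosing period for the same days is 4 months in two places and 6 in the third, where the parts do not add up to the stated total.

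The consequence is limited. At most 20 participants could be concerned. The data exposed are exploratory CMI, safety and descriptive antibody results. Both Part B primary neutralizing antibody endpoints are in transplant recipients and are unaffected. Any deviation depends on a site scheduling from the synopsis or section 3.1.1 instead of the schedule of events, and its frequency cannot be estimated from the documents. The conclusion assumes dose 2 on its nominal day. Within the -3/+7 day window the Day 129 interval is 93 to 103 days, and the conclusion does not change.

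**What to change.** The sponsor should:

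1. Reconcile the healthy cohort's booster day across the synopsis (Study Periods and Study Duration), section 3.1.1 and Table 10, and reconcile all of them with criterion 1a in section 4.2.1, section 3.1.1.2 and Table 10 footnote 1. Which day or interval applies is for the sponsor to decide.
2. Correct the dosing-period and total-duration text to match. The same synopsis block gives Group B2 about 9 months of dosing, against 7 elsewhere, and should be checked together with it. Correct the group label on the 3-dose transplant paragraph in section 3.1.1.
3. In SAP sections 5.3.2 and 5.3.3, tie the on-schedule booster condition to the reconciled Part B schedule by table number, and replace the Table 18 reference in SAP Appendix E.

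The cost is a clarification memo or amendment wording and a small SAP edit. No visits, samples or analyses are added.
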